The secondary objective of this study is to determine if skin-to-skin contact (i.e., family bond initiation) occurs earlier and in-hospital breastfeeding initiation is more likely with the family-centered cesarean delivery method than traditional cesarean delivery method.

Tertiary Objective

The tertiary objective of this study is to determine if differences in maternal and neonatal outcomes exist between cesarean delivery methods (family-centered versus traditional cesarean).

III. STUDY DESIGN

Subject Enrollment

[figure not shown]
Women undergoing a scheduled cesarean delivery at ≥ 38 weeks of gestation who present at Aurora Sinai Medical Center and Aurora BayCare Medical Center and have their babies delivered by obstetrics and gynecology physicians during June 1, 2016 through May 31, 2019 will be enrolled in this study. Patients who meet the study criteria will be recruited via obstetrics and gynecology physicians on the day of their scheduled cesarean section. Patients who agree to participate in this study will be formally consented. The study will be described to the patient using the following script, containing objective language so as to minimize bias or influence when the patient is later asked to identify her preference of the 2 cesarean delivery methods. Note that Method 1 below describes the family-centered delivery method, while Method 2 describes the traditional delivery method.

“We are conducting a patient satisfaction study on two methods of cesarean section. Both of these methods are used throughout the United States, and neither has been proven to be better than the other. Method 1 involves lowering part of the surgical drape exposing a transparent window through which you can watch the birth of your baby; the baby will be placed on your chest immediately after the delivery. Cleaning and evaluation of your baby will be done by a nurse who is standing next to you at the head of the bed. Method 2 involves keeping the surgical drape up throughout the entire surgery so that the birthing process will not be visible, and your baby will be taken to the warmer to be evaluated and cleaned after birth but is available to be laid on your chest at any point upon request.”

Randomization to Method

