Eligible patients will be formally consented on the day of their scheduled cesarean sections by the research coordinator, resident physician(s), charge nurse or nurse. Following enrollment, each patient will be asked to state which method of cesarean delivery she would prefer, if given the option to choose. Preference represents a potential factor influencing patient satisfaction that will be later incorporated into the statistical analysis, based on a 2 x 2 factorial (Method x Preference) design. Documentation of preference at this time (versus following random assignment to cesarean delivery method) is important for minimizing the bias or influence of the random assignment upon the patient’s declared preference.

The patient will be randomized to 1 of the 2 delivery methods by the research coordinator, resident physician(s), charge nurse or nurse, who will present the patient with a sealed envelope. The envelope will contain a slip of paper identifying the patient’s random assignment to either the family-centered cesarean delivery method (Method 1) or the traditional delivery method (Method 2). Fifty percent of all envelopes preassembled for patients will contain paper slips stating “Family-centered”, while the remaining 50% will contain slips stating “Traditional,” allowing for a 1:1 allocation of delivery methods.

Assessment of patient satisfaction following delivery

The primary objective of this study is to compare levels of patient satisfaction with the birthing experience between the two cesarean delivery methods. To assess patient satisfaction, each patient will be verbally surveyed by the study coordinator using an 11-item questionnaire. Similar to the questionnaire used by Armbrust and his colleagues⁶, items on our questionnaire will relate specifically to the mother's birthing experience and answers available per item will be in the form of a modified Likert scale, ranging from 1, the lowest level of agreement or degree of satisfaction, to 5, the highest level of agreement or degree of satisfaction. The survey questions will be asked before discharge (approximately within 48 hours after the delivery), to allow sufficient opportunity for the mother and newborn to bond before discharge.

IV. STUDY POPULATION

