In our study, a factorial design with 2 design variables (Cesarean Delivery Method [Gentle, Traditional] and Preference of Method [Gentle, Traditional]) will be used. A sample size of 508 total patients (127 patients in each of the 4 Method x Preference combinations) has been determined necessary to detect a 0.5-point difference in mean satisfaction scores (on a 5-point scale) and a 15-minute difference in time-to-initiation of family bond between the 2 groups of each design variable, given 2-factor generalized linear modeling with normally-distributed (or log-transformed) responses, standard deviation of 2 points (for satisfaction score) and 1-hour (for family bond initiation), alpha of 0.05, and power of 0.80. Moreover, to detect a 15% difference in probability of breastfeeding prior to discharge between the 2 groups of each design variable using logistic regression, a sample size of 432 total patients (108 patients in each of the 4 Method x Preference combinations) would be necessary. To detect clinically-relevant differences for all outcomes (responses) of interest in the Primary and Secondary Objectives, we will target 508 total patients.

VI. DESCRIPTION OF DELIVERY METHODS

Method 1: Family-centered cesarean

Standard preoperative preparation will be performed in the patient's room, including surgical site hair clipping, chlorhexidine wash (at ASMC only), IV placement, completion of pre-procedure operating room checklist, and administration of prophylactic antibiotics, antiemetics (at ASMC only), and fluids. The patient will then be taken to the operating room. The pulse oximeter will be placed on the mother, and the electrocardiogram leads will be placed away from anterior chest wall or via an EKG back-patch to allow space for newborn and mom skin contact. Regional spinal anesthesia will be administered in normal fashion. The mother will lie down on the bed and, once sufficient anesthesia block is obtained, her gown will be removed and a blanket will be provided for her to cover her chest, allowing for easier skin-to-skin contact after delivery. Prior to the lowering of the drape, the mother's head will be elevated. Fetal heart tracing will be monitored until adequate block is obtained to confirm fetal well-being.

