Preoperative preparation will continue with abdomen preparation. We will then wait 3 minutes from wash to dry before placing the blue drape on the mother's abdomen and attaching it to the IV poles, thereby screening the mother from the entire surgery. After delivery, the newborn will be handed off to a nurse waiting at the side of the mother who will take the newborn to the warmer on the opposite side of the operating room. The newborn will be dried and warmed with fresh towels on the warmer, while being evaluated by the nurse and respiratory therapist per hospital cesarean section protocol. The nurse will then proceed with newborn measurements, weight, bath, and administration of vitamin K and erythromycin ointment. The newborn will be swaddled and kept in the warmer until the mom requests that the newborn be brought to her or until the surgery has been completed and the mom is ready to be transferred to the recovery room.

VII. DATA COLLECTION

Patients will be followed throughout their hospital stay. The following variables of interest will be retrospectively collected from EPIC or recorded during the surgery on the OR Worksheet (* - Note, the OR Worksheet was updated on 2/16/2018.):

Maternal Variables of Interest

- Medical record number
- Date of birth
- Delivery Hospital (0=ASMC; 1=ABMC)
- Date of consent for scheduled cesarean section
- Date of procedure
- Calculated maternal age
- Race
- Ethnicity
- Gravidity (Gx)
- Parity (Pxxxx)
- Gestational Age (XwXd)
- Height (inches)
- Weight (lbs)
- Calculated BMI (kg/m²)
- History of previous vaginal delivery (0=No; 1=Yes)
- History of previous cesarean delivery (0=No; 1=Yes)
- Reason for previous cesarean delivery
- History of previous abdominal/pelvic surgery (0=No; 1=Yes)
- Reason for planned cesarean delivery
- Type of cesarean delivery technique (0=Family-centered; 1=Traditional)
- Identified mother preference (0=Family-centered; 1=Traditional)
- Type of cesarean delivery (0=NA; 1=Classical; 2=Low Transverse)
- Type of skin incision (0=NA; 1=Pfannenstiel; 2=vertical)
- Operative start time (00:00:00)
- Operative stop time (00:00:00)
- Duration of operation (minutes)
- Estimated blood loss (mL)
- Hemorrhage EBL >1000mL (0=No; 1=Yes)
- Complications occurred (0=No; 1=Yes)
- Type(s) of complication(s) that occurred
- If the mother's delivery technique was family-centered, was she switched to a traditional cesarean? (0=No; 1=Yes)*
- Was mom offered to view the birth of her baby? (0=No; 1=Yes)*

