- If offered to view the birth of her baby, was the drape dropped? (0=No; 1=Yes)*
- Was mom/other support person offered baby right away? (0=No; 1=Yes)*
- Physician Name
- Did family bond occur in the OR? (0=No; 1=Yes)*
- Time from birth to initiation of family bond (minutes)*
- Person who initiated family bond (0=Mother; 1=Father; 2=Other Support Person)*
- Family bond interrupted in the OR (0=No; 1=Yes)*
- Reason family bond interrupted in the OR*
- If the family bond DID NOT occur, why not?*

-
- Surgical site infection associated with this surgery (0=No; 1=Yes)
 - Time to skin-to-skin contact & all other related skin-to-skin variables identified
 - Breastfeeding status flowsheet data (3=Unknown; 2=No; 1=Yes)

Neonatal Variables of Interest

- Birth weight
- 1-min APGAR
- 5-min APGAR
- Documented neonatal infection (0=No, 1=Yes)
- Newborn heart rate at 10 minutes*
- Newborn respiratory rate at 10 minutes*
- Newborn temperature at 10 minutes*
- Time taken for newborn to reach oxygen saturation >90%*

Assessment of patient satisfaction will be conducted following delivery. Questions from an 11-item questionnaire will be asked of the patient by the study coordinator, [name], or one of the resident physicians or the nurses/charge nurses at ASMC and study coordinator, [name], or one of the nurses or charge nurses at ABMC. Please see the questionnaire displayed in a separate document.

Please note, that while we aim to obtain the OR worksheet and patient satisfaction survey from all patients enrolled in the study, there may be circumstances in which one or the other were not completed. If a patient has either the OR worksheet or the patient satisfaction survey completed, we will not exclude them from the study/analyses, but it will be adjusted for.

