We will perform interim analyses throughout the study. In order to identify those individuals who may not have been asked to participate within our study or who did not participate within our study (we will not know specifically who declined or who was not asked to participate), we are requesting data from our Quality Teams, within our labor and delivery units, and Research Analytics. Individuals who were classified as scheduled or planned non-emergent (green or yellow) cesarean deliveries will be identified, as planned emergent (those deemed red) cesarean deliveries are not eligible for the study. Additionally, all variables of interest identified above may be requested in addition to variables of interest that would allow us to further determine whether a patient was ever eligible for the study (see study inclusion and exclusion criteria).

Please note, the OR Worksheet and patient satisfaction surveys were updated on 2/16/2018. Based on our interim analyses, we have decided to change the OR worksheet and patient satisfaction surveys to further clarify how we want data to be collected/recorded. Our biostatistician carefully reviewed the changes to make sure that we are acquiring the same information, but in a clearer manner (i.e., there is less room for interpretation). Furthermore, changes on the translated patient satisfaction survey were reviewed by a certified Aurora Translator, who verified that the document was clear/the changes made are appropriate.

VIII. STATISTICAL PLAN

To describe our study population and assess equivalency in characteristics among patients in the 4 Method x Preference combinations, we will compute frequencies, means with 95% confidence intervals, and medians with interquartile ranges, as appropriate per variable type. Differences among the groups will be tested using the Pearson chi-squared test of independence, Student's t-test, or Wilcoxon's rank sum test, respectively. To generally describe the outcomes (responses) corresponding to each of our 3 study objectives, both within and across the 4 Method x Preference combinations, we will again compute frequencies, means with 95% confidence intervals, and medians with interquartile ranges, as appropriate per variable type.

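### The satisfaction survey was revised 57% of the way through the enrollment window and the planned models pool both versions; a form-version term would be a cheap, optional improvement

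*Combined protocol and SAP*

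**What the plan says.** - **Window.** Section III (Subject Enrollment) covers women delivered "during June 1, 2016 through May 31, 2019 will be enrolled in this study".
- **Form change.** Section VII says "the OR Worksheet and patient satisfaction surveys were updated on 2/16/2018". It adds that interim analyses prompted the change, that the aim was clearer recording, that the biostatistician checked that the same information is still acquired, and that a certified translator reviewed the translated survey.
- **Primary outcome.** Section III (Assessment of patient satisfaction following delivery) measures it with an 11-item survey, each item scored 1 to 5.
- **Models.** For each outcome, Section VIII fits Method, Preference and their interaction as fixed effects, with a random intercept for physician nested within hospital. Survey items are modeled as multinomial, with results read as odds ratios. No version term, period term or before/after analysis is mentioned.
- **The only other adjustment.** For patients with just one of the two forms completed, Section VII says "we will not exclude them from the study/analyses, but it will be adjusted for". That concerns a missing form, not a changed one.
- **Preference.** It is declared, not assigned: "Following enrollment, each patient will be asked to state which method of cesarean delivery she would prefer". Section V nevertheless sizes the trial for both factors, including "a 15-minute difference in time-to-initiation of family bond between the 2 groups of each design variable".

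**The concern.** If a form is changed so that it can be read in fewer ways, some respondents may have read the old form differently. Answers before and after 2/16/2018 may then differ for reasons unrelated to the delivery. The biostatistician's review supports sameness of content; it does not show that the answers are comparable.

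Pooling without a version term puts any such shift into the residual, which costs precision. It could also put part of the shift into the effect of any factor whose mix changed over the three years. Randomization prevents that for Method, apart from chance imbalance. It does not for Preference, which Section V also powers. Readers would also be unable to see whether the primary result looks alike under the two versions.

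**Working it through.** **Inputs from the plan.** Window 6/1/2016 to 5/31/2019 (Section III); change on 2/16/2018 (Section VII); difference 0.5 point, SD 2, alpha 0.05, power 0.80, N = 508, or 254 per level of each factor (Section V). The size of any version shift, the accrual pattern and any drift in preference are not given; the values used for them below are assumptions.

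**1. The plan's sample size.** n per level = 2(1.96 + 0.842)² × 2² / 0.5², which rounds up to 252, or 504 in total. The t-based solution is 252.13, so 253 per level and 506 in total. Rounding up to four equal cells gives 4 × 127 = 508, the stated figure. Power at 254 per level = Φ(0.5 / (2√(2/254)) − 1.96) = 0.804.

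**2. Timing.** 625 / 1,094 days = 0.571. Under uniform accrual, 508 × 0.571 ≈ 290 patients precede the change and 218 follow it.

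**3. Precision of the Method effect.** An unmodeled common shift d adds 0.571 × 0.429 × d² = 0.245d² to the variance.

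| SD | Shift d | Added variance | Power for 0.5 point |
|---|---|---|---|
| 2.0 | 0 | none | 0.804 |
| 2.0 | 0.5 | 1.5% | 0.798 |
| 2.0 | 1.0 | 6.1% | 0.781 |
| 1.5 | 0 | none | 0.964 |
| 1.5 | 1.0 | 10.9% | 0.946 |
| 1.0 | 0 | none | above 0.999 |
| 1.0 | 1.0 | 24.5% | 0.999 |

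An SD of 2 is the most a 1-to-5 scale allows (half the answers at each end: √(2 × 2) = 2), so the SD 2 rows are a formal calculation at the plan's own value. With smaller SDs the relative inflation is larger, but power is already well above 0.80.

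**4. Pooled odds ratio.** I fitted a proportional-odds model to expected counts, with five levels, either flat or skewed (2/3/10/25/60%), and a within-version Method odds ratio of 1.50. Omitting a version odds ratio of 1.5 lowers the pooled log odds ratio by about 1%; omitting one of 3 lowers it by about 5% to 6%, so that 1.50 becomes about 1.46 to 1.47.

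**5. Preference effect.** Bias = d × [P(late | prefers family-centered) − P(late | prefers traditional)].
- No drift: zero.
- Share preferring family-centered rises from 60% to 70%: 0.467 − 0.360 = 0.107, so d = 0.5 to 1.0 gives 0.05 to 0.11 point.
- Share rises from 60% to 80%: 0.500 − 0.273 = 0.227, so 0.11 to 0.23 point.

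**6. What a by-version comparison can show.** SE of the log odds ratio = √(12 / (n(1 − Σp³))), with equal groups and clustering by physician ignored.
- n = 290: SE 0.208 (flat) to 0.232 (skewed); the 95% CI extends a factor of exp(1.96 × SE) = 1.50 to 1.58 each way.
- n = 218: SE 0.239 to 0.268; factor 1.60 to 1.69.

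On the mean scale, a version-by-Method interaction has SE √(16/290 + 16/218) ≈ 0.36, which gives about 29% power for a 0.5-point interaction.

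**The case against.** The strongest reply is that the primary objective is safe. The comparison is between randomized methods, a shift common to both arms falls equally on each in expectation, and the power cost is at most about two percentage points. This stands, and it limits the point to an improvement.

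Four stronger readings are tempting, and the documents do not support them.

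- *The pooled odds ratio is biased toward 1.* The shrinkage in step 4 is non-collapsibility: odds ratios averaged over versions and within versions are different quantities, even under perfect randomization.
- *The Preference effect is confounded.* That needs both a real version shift and a drift in stated preference. Neither is documented. Preference is asked after a fixed, neutral script, and Section II does not list it as an objective. It would remain an observational contrast even with a version term.
- *The old form diluted the Method effect and cost power.* Nothing shows that the Method effect differs by version. The forms are in a separate document and cannot be compared here.
- *Family-bond time changed definition.* Section VII stars that item in connection with the updated worksheet, but the star may only mark items taken from the worksheet. The separate entry "Time to skin-to-skin contact & all other related skin-to-skin variables identified" is unstarred, although Section II equates skin-to-skin contact with family bond initiation. Whether the secondary outcome is touched at all is therefore unclear.

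It is also fair to say that pooling is inferred from silence, and that a version term cannot separate a form effect from calendar time. Neither argues against including so cheap a term.

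**Conclusion.** The point holds as a low-cost, optional improvement. The primary-outcome survey changed at 57% of the window by calendar time, and Section VIII provides no way to separate the versions. Material bias in the Method effect is not expected from a shift common to both arms. At the plan's SD, an assumed 0.5 to 1.0 point shift takes power from 0.804 to 0.798 or 0.781. Possible bias in the Preference effect is 0.05 to 0.23 point under the assumed shifts and drifts, and zero without drift.

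The 57% is a share of calendar time; the 290/218 split assumes uniform accrual. The survey part rests on the plain statement that the surveys were changed. The worksheet part is conditional on which items were revised.

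**What to change.** In Section VIII:

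1. Add form version as a fixed effect in the satisfaction-item models. Use the version actually completed or, if that was not recorded, before versus on or after 2/16/2018 by date. State that the term also absorbs calendar time.
2. Add the same term to the family-bond-time model, or to another worksheet outcome, only if the sponsor confirms that the item was revised. Listing the revised items in Section VII would settle this.
3. As a descriptive sensitivity check, report the Method odds ratio with 95% CI by version for the satisfaction items. Use no interaction test as a decision rule, given its low power.

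**Cost.** About 1 degree of freedom per cumulative-odds model, or up to 4 per five-level item if effects vary by category. There is one supplementary table (11 items × 2 versions = 22 rows) with wide intervals, which can neither establish nor refute comparability. No new data are needed, because "Date of procedure" is already collected. The survey is given within about 48 hours of delivery, so dating it by procedure would misassign about 2 × 508 / 1,094 = 0.93, or one, patient.

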To improve the overall child birthing experience, the family-centered/gentle cesarean delivery method mimics a vaginal birthing experience. Similar to a vaginal delivery, a mother can watch the birth, and the newborn is immediately placed on the mother's chest following cesarean delivery. Studies have shown that immediate mother-newborn interactions and skin-to-skin contact is advantageous in promoting the bond between mother and newborn, breastfeeding, and overall patient satisfaction with the birthing process.^{1, 5} The family-centered/gentle cesarean method is relatively new. Limited information is available in regards to differences in maternal and neonatal outcomes when comparing traditional cesarean methods to that of the family-centered/gentle cesarean. Additionally, available information often refers to this methodology as either family-centered cesarean or gentle cesarean; we will refer to this method as the family-centered cesarean from here on out.

One European study conducted in Germany compared family-centered and traditional cesarean delivery methods, and determined that no additional complications arose for mother or newborn when using the family-centered cesarean method.⁶ Although the Memorial Hospital of Rhode Island has implemented the family-centered cesarean method as the standard of care during cesarean delivery, to our knowledge, no studies have been conducted in the United States that compare the family-centered cesarean method to traditional methods of cesarean delivery.⁴ Magee et al. further supports that the techniques used in their hospital have not been evaluated and that the hospital's approach to family-centered cesarean deliveries should be further examined as it relates to maternal and neonatal outcomes, as well as overall patient satisfaction.⁴

The purpose of this study is to determine if patient birthing experiences differ between the family-centered and traditional cesarean methods. We hypothesize that the family-centered cesarean method will lead to more unique and personalized cesarean birthing experiences without increasing the risks of adverse neonatal and maternal outcomes from those documented

with the traditional cesarean.

II. SPECIFIC AIMS

Primary Objective

The primary objective of this study is to compare patient satisfaction of the family-centered cesarean birthing experience with that of the traditional cesarean experience.

Secondary Objective

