For each outcome of interest, we will also develop a mixed regression model to examine the fixed main and interaction effects of Method and Preference. All models will be structured with appropriate response distributions, likely including the lognormal (normal distribution with natural log-transformed response) for continuous responses (e.g., time, weight, vitals), multinomial for survey questions of satisfaction, and binomial for 2-category outcomes (e.g., breastfeeding). Following back-transformation or exponentiation of parameter estimates, model results will be interpreted, respectively, as the percentage difference between groups, ratio of odds of a lower value, and ratio of odds of an outcome occurring. Unobserved outcome heterogeneity will be captured by the delivering physician nested within hospital, each combination of which will define a separate random variable and model intercept.

IX. POTENTIAL RISKS AND BENEFITS

Risks associated with Method 1 (family-centered cesarean delivery) include unforeseen patient and/or family discomfort with viewing the surgical field. Patients will be made aware of the potential risk of such discomfort prior to consenting to participating in the study. Notably, risks of this nature are a normal component of any cesarean delivery. Therefore, we will discuss the risk of viewing discomfort with all patients regardless of study participation. An additional risk associated with participating in either method could be loss of confidentiality due to obtaining limited protected health information. However, to minimize risk, all data will be stored on a password protected computer.

A potential benefit of our study is that we may be able gather level-1 evidence to support local, regional, and possibly broader use of a novel method of cesarean delivery, currently being explored nationally and internationally. We hypothesize that there will be improved maternal satisfaction using the family-centered method. We also hypothesize that neonatal morbidity will not be increased and benefits may include earlier skin-skin contact and greater likelihood of breastfeeding.

X. REFERENCES

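### Section VIII does not name the primary Method contrast, so with Method x Preference in the model neither the overall comparison nor its 0.80 power is assured

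*Combined protocol and SAP*

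**What the plan says.** The primary objective (Section II) is to "compare patient satisfaction of the family-centered cesarean birthing experience with that of the traditional cesarean experience". This is one overall comparison between the randomised groups.

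Section V plans "A sample size of 508 total patients (127 patients in each of the 4 Method x Preference combinations"). For satisfaction the aim is to "detect a 0.5-point difference in mean satisfaction scores (on a 5-point scale"); for family-bond initiation the target is a difference of 15 minutes. Alpha is 0.05 and power 0.80. Each contrast is a two-group one, "between the 2 groups of each design variable, given 2-factor generalized linear modeling". No power is stated for an effect within one preference group or for the interaction.

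Section III (Randomization to Method) has each woman state her preference before she opens a sealed envelope, with 1:1 allocation to Method. It describes no stratification by preference, no quota and no expected split.

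Section VIII fits, for each outcome, "a mixed regression model to examine the fixed main and interaction effects of Method and Preference", with random intercepts for physician within hospital. It adds: "Following back-transformation or exponentiation of parameter estimates, model results will be interpreted" as percentage differences or odds ratios. It gives no contrast coding, no weighting of the preference groups, no rule for the interaction term and no statement of which Method contrast is primary.

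**The concern.** Once Method x Preference is in the model, the Method parameter has no single meaning. Under reference coding it is the Method effect among women in the reference preference group only. Under sum-to-zero coding it is the simple average of the two group-specific effects, whatever the group sizes. It equals the overall effect in the randomised women only if preference splits evenly or the Method effect is the same in both groups.

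Two analysts could both follow Section VIII and report different headline estimates. The plan itself treats preference as something that may influence satisfaction, so a differing effect cannot be ruled out. As an illustration with assumed values, take an 80/20 split with effects of +0.7 and -0.3:

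- Overall effect: 0.8 x 0.7 + 0.2 x (-0.3) = 0.50.
- Equal-weight effect: (0.7 - 0.3)/2 = 0.20.
- Reference-coded effect: +0.7 or -0.3, depending on the reference group.

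Precision is also at stake. Both versions of the parameter can have a larger standard error than the contrast that Section V powers.

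**Working it through.** **Inputs (Section V).** Difference d = 0.5 points, SD = 2, alpha = 0.05, power = 0.80, N = 508, so 254 per Method. Sidedness is not stated; two-sided testing reproduces the plan's figure. The family-bond inputs (15 minutes, SD 60 minutes) give the same ratio d/SD = 0.25, so the same results apply to them.

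**Reproducing 508.** n per Method = 2 x (1.960 + 0.842)^2 x 2^2 / 0.5^2, about 251.2, so 252, or 504 in total. The t-based figure is 252.13, so 253 per Method and 506 in total. Rounding up to four equal cells gives 508. Power at 508 (non-central t, 504 df) is 0.803. Section V's number is sound for the contrast it describes.

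**Three Method effects at N = 508.** Let p be the share of women in the larger preference group, equal in both arms, and let the true Method effect be 0.5 in both groups.

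1. *Method + Preference, no interaction:* SE = 2 x sqrt(2/254) = 0.177 at any p. Power is 0.803.
2. *Equal-weight main effect from the interaction model:* SE = 0.5 x sqrt(SE1^2 + SE2^2), where SE1 = 2 x sqrt(2/(254p)) and SE2 = 2 x sqrt(2/(254(1-p))).
3. *Reference-coded Method parameter:* SE1 if the reference is the larger group, SE2 if it is the smaller.

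| Assumed split | Additive | Equal-weight SE | Equal-weight power | Reference = larger group | Reference = smaller group |
|---|---|---|---|---|---|
| 50/50 | 0.80 | 0.177 | 0.80 | 0.51 | 0.51 |
| 60/40 | 0.80 | 0.181 | 0.79 | 0.59 | 0.43 |
| 70/30 | 0.80 | 0.194 | 0.73 | 0.65 | 0.34 |
| 80/20 | 0.80 | 0.222 | 0.61 | 0.71 | 0.24 |
| 90/10 | 0.80 | 0.296 | 0.39 | 0.76 | 0.14 |

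A least-squares simulation (4,000 trials at each of 50/50, 70/30, 80/20 and 90/10) agrees. The additive model gave 0.80, 0.80, 0.81 and 0.81; the sum-to-zero main effect gave 0.80, 0.72, 0.61 and 0.38.

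**Sample size to recover 0.80.** The equal-weight effect needs 504/(4p(1-p)): at 80/20, 504/0.64 = 787.5, so 788; at 90/10, 504/0.36 = 1,400. The reference-coded parameter at equal cells needs 504/0.5 = 1,008.

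**The case against.** The strongest reply is that in a 2 x 2 factorial the term main effect normally means an effect averaged over the other factor, and that Section V's wording fits that reading. At the planned 127 per cell, the averaged effect has power 0.80 and coincides with the overall effect. On that reading nothing is lost under the plan's own layout.

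This stands as far as it goes. A reader might infer that the plan reports the effect in one preference group, or that its 0.80 power is lost outright. The documents support neither. Section VIII does not state reference coding, and the 0/1 codes in Section VII are data-entry codes. All the unequal splits above are assumptions.

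What remains is that equal cells are planned but not secured, because women choose their own preference. The averaged reading also has to be supplied by the reader, while Section VIII speaks of parameter estimates.

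Two further limits stand:

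- The power figures assume a constant Method effect. In that case, on the linear scale, all codings target the same quantity and differ only in precision. The shift in target arises when the effect differs by preference, and the figures above do not then apply to the one-group and equal-weight contrasts.
- The figures use Section V's normal model. Section VIII plans a multinomial model for the satisfaction items, a binomial model for breastfeeding, and physician intercepts with no stated variance. The ambiguity carries over to those models; the exact powers do not.

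Fitting the interaction is itself defensible. The difficulty lies in reading the primary result from that model without naming the contrast.

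**Conclusion.** The concern holds in conditional form. Section VIII leaves the primary Method contrast undefined in a model where the Method parameter is either a one-group effect or an equal-weight average. The overall comparison and its 0.80 power are therefore not assured, which is different from their being shown to fail.

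Under sum-to-zero coding and Section V's assumptions, the loss is nil at 50/50 and about 2 points at roughly 62/38. Power falls to 0.73, 0.61 and 0.39 at assumed splits of 70/30, 80/20 and 90/10. Under reference coding it is 0.51 even with the planned equal cells. An additive model avoids both losses at every split. The change should be made, because it is nearly free and ties the estimate to the stated objective.

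**What to change.** In Section VIII, name one confirmatory Method effect for the primary and secondary outcomes: the Method coefficient from a model with Method and Preference, the planned physician-within-hospital random intercepts, and no interaction.

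A contrast standardised to the observed preference proportions is a possible alternative. It is not equivalent in the multinomial and binomial models, because odds ratios are non-collapsible, so only one of the two should be named.

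Report Method x Preference, and the Method effect within each preference group, from a second, separate model. State that the Method parameter of the interaction model is not the primary result.

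The cost is one paragraph before the final analysis, with no new patients or data. Section VII says interim analyses are performed during the study, so the contrast should be fixed and dated before further results are seen. The small downside is that the overall effect averages over the preference groups if the effect truly differs between them; the second model shows this.
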